6.1.2 Dose Escalation Protocol

A standard 3+3 dose escalation strategy will be used. The table below shows the doses that will be provided. Three participants will be initially enrolled at Level 1. If none of the first three participants at a given dose experiences dose-limiting toxicity (DLT), the dose will be escalated. If two or more of the first three participants experience DLT, the prior dose will be deemed the maximum tolerated dose (MTD) and the study will be terminated. If one of the first three participants experiences DLT, an additional three participants will be enrolled at the same dose. If among these six, only one experiences DLT, the dose will be terminated. If two or more of six experience DLT, the prior dose will be deemed the MTD and the study will be terminated. If the MTD is reached and only three participants have been treated at that dose, an additional three will be treated to ensure six subjects are treated at the MTD. DLT are defined in Section 4.1.1 (Primary Study Endpoints: Feasibility and Safety).

| Dose Level | Freeze Time (per site) | Thaw Time |
|------------|------------------------|---|
| Level 1 | 1 second | Will last until the probe separates from target tissue* |
| Level 2 | 2 seconds | Will last until the probe separates from target tissue* |
| Level 3 | 3 seconds | Will last until the probe separates from target tissue* |
| Level 4 | 5 seconds | Will last until the probe separates from target tissue* |
| Level 5 | 10 seconds | Will last until the probe separates from target tissue* |
| Level 6 | 20 seconds | Will last until the probe separates from target tissue* |

CONFIDENTIAL

| Level 7 | 30 seconds | Will last until the probe separates from target |
|---------|------------|---|
| | | tissue* |

6.1.3 **Procedures for Training of Clinicians on Procedural Intervention**

The NYU Interventional Pulmonary service has extensive experience using the flexible cryoprobe for debulking of central airway tumors. BCI will be performed by a board-certified, NYU Interventional Pulmonologist.

Only patients with the presence of a bronchus or airway path leading directly to the peripheral lung tumor will be eligible to undergo BCI. The peripheral tumor will also need to be identified by radial EBUS prior to performing BCI. If the peripheral tumor is unable to be identified by radial ultrasound within 20 minutes, then the patient will not be a candidate to undergo BCI.

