| Population | Patients with known or suspected advanced non-small cell lung cancer (stages IIIA/B/C and IVA/B based on the 8th edition TNM staging), with an accessible peripheral lung tumor, and who have been referred to NYU Interventional Pulmonary for bronchoscopy for diagnostic and/or palliative purposes unrelated to this study Patients with high risk clinical features (significant smoking history, history of COPD, presence of spiculated lesion with bronchus sign on chest CT, enlargement of mediastinal/hilar lymph nodes and/or evidence of distant metastatic disease) may be candidates for BCI if they meet all other enrollment criteria. Age: > 22 years of age Gender: All genders ECOG performance status ≤ 2 Location: New York, New York | |
|--------------------------------|--|--|
| Study Sites | New York University Langone Medical Center | |
| Number of participants | Up to 24 participants | |
| Description of Intervention | BCI is performed by advancing a flexible cryoprobe through a bronchoscope to reach a target peripheral tumor. Freeze-thaw cycles will be applied to the target peripheral tumor with the intention of inducing anti-tumor immune responses. The number of freeze-thaw cycles will depend on the size of the target tumor. One freeze-thaw cycle will be applied per one centimeter of largest tumor diameter. Providers will be instructed to remain greater than 2 cm away from critical structures. Freeze times will start at 1 second, and will be increased by dose-escalation protocol based on tolerability. The thaw phase will last until the cryoprobe separates from the target tumor. | |
| Reference Therapy | | |
| Key Procedures | Bronchoscopic Cryo-Immunotherapy Bronchoalveolar lavage in the lobe regions of the primary tumor and of the distal portion of the same lung Pre-BCI (day 0) and Post-BCI (day 7 and day 14 ± 3) blood draws | |
| Statistical Analysis | A standard 3+3 dose escalation design will be implemented. Safety endpoints, including the incidence of bleeding and pneumothorax, will be descriptive. Wilcoxon signed-rank tests will be used to assess paired pre- and post-BCI biomarker levels. | |

Schematic of Study Design

1 Key Roles

Principal Investigator:

[name]

Director, Division of Pulmonary, Critical Care, and Sleep Medicine New York University School of Medicine [name] [contact] [contact]

Additional Investigators:

[name]

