10.4.3 Analysis of the Primary Endpoint: Safety

Safety endpoints will be descriptive in nature, and any possible, probable, or definite adverse event will be counted only once for a given participant. Frequency and severity of all adverse events will be reported, both in the total study population and stratified by dose level.

Dose-limiting toxicities will be tabulated in the whole population and by dose level. Bleeding severity will be graded based on severity scale as described in Section 4.1.1 (Primary Study Endpoints: Feasibility and Safety). Pneumothoraces will be reported and described based on size, associated

CONFIDENTIAL

symptomatology and respiratory impairment, and need for chest tube placement. Length of time to perform BCI and length of time of fluoroscopy exposure during BCI will be reported in minutes. Other adverse events will be recorded and categorized as per the NCI Common Terminology Criteria for Adverse Events (CTCAE) (33).

The maximum tolerated dose (MTD) will be determined based on the dose escalation rules described below and in Section 6.1.1. The MTD is the dose at which fewer than 1 of 3 or at most 1 of 6 participants on that dose experience a DLT.

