10.5 Sample Size

We will aim to enroll approximately 24 patients. The exact number will be determined based on our dose escalation protocol (as described in section 6.1.2).

The table below gives the operating characteristics of this design, presenting the likelihood of escalation when the true DLT rate takes various values. For example, if the true DLT rate is 60%, the probability of escalation is only 0.08. If the true DLT rate is 10%, the probability of escalation is 0.91.

| True DLT Rate | 10% | 20% | 30% | 40% | 50% | 60% | 70% | 80% | 90% |
|---------------------------|------|------|------|------|------|------|------|--------|--------|
| Probability of Escalation | 0.91 | 0.71 | 0.49 | 0.31 | 0.17 | 0.08 | 0.03 | <0.001 | <0.001 |

The small sample size will not provide sufficient power to definitively address the secondary endpoint of measuring BCI induced anti-tumor immune responses. For example, 15 subjects provide approximately 80% power to detect a difference of about 0.75 standard deviations between pre- and post-BCI peripheral blood CD8⁺ T cell expression of PD-1 and Ki67, conservatively assuming a within-subject correlation between assessments of 0.5. However, our results will be critical for informing the design of further studies aimed at estimating response and survival rates with BCI combined with anti-PD1- therapy for the treatment of advanced non-small cell lung cancer.

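### Section 6.1.2 gives no usable instruction after 1 DLT in 6: it says the dose is terminated, while the table in 10.5 counts that result as escalation

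*Combined protocol and SAP*

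**What the plan says.** Section 6.1.2 opens with "A standard 3+3 dose escalation strategy will be used" and then takes the outcomes one by one. No DLT in three leads to the next level. One in three adds three participants at the same level. Two or more in three makes the prior dose the MTD and ends the study. For the expanded cohort there are two sentences. The first is "If among these six, only one experiences DLT, the dose will be terminated". The second is "If two or more of six experience DLT, the prior dose will be deemed the MTD and the study will be terminated".

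Section 10.4.3 says the MTD follows from the "dose escalation rules described below and in Section 6.1.1", and defines the MTD so that at most 1 DLT in 6 is acceptable. Section 6.1.1 describes how the procedure is given and holds no escalation rule. Section 8.4 stops for DLTs only at two or more at a level.

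Section 10.5 tabulates the probability of escalation for true DLT rates of 10% to 90% and works two examples: "If the true DLT rate is 10%, the probability of escalation is 0.91", and "if the true DLT rate is 60%, the probability of escalation is only 0.08". The Protocol Summary sets enrolment at "Up to 24 participants".

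**The concern.** The 1-of-6 sentence is the only outcome in 6.1.2 that lacks a next step. It can mean that the level is complete and the next one opens, or that escalation ends. The sentences on either side use the same verb for stopping the study, so a literal reader could well stop.

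Determining the MTD is part of the primary objective, and 6.1.2 is where staff look after a DLT. If they stopped at 1 of 6, they would stop on a result that 10.5 counts as a pass. The operating characteristics in 10.5 would then describe a different design from the one being run. The MTD for that branch would also have to be inferred.

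**Working it through.** **Inputs.** The branch rules come from 6.1.2, the printed probabilities and worked examples from 10.5, the seven levels from 6.1.2, and the limit of 24 from the Protocol Summary. Write p for the true DLT rate at a level and q = 1 − p.

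**Step 1: reproduce the table in 10.5.** A level can be passed in two ways:

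- 0 DLT in 3: a = q³
- 1 DLT in the first 3, then 0 in the next 3: b = 3pq² × q³ = 3pq⁵

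If 1 of 6 escalates, P(escalation) = a + b. If 1 of 6 stops, P(escalation) = a. At p = 0.10, a = 0.9³ = 0.729 and b = 3 × 0.1 × 0.9⁵ = 0.177, so a + b = 0.906.

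| True DLT rate | Printed in 10.5 | 1 of 6 escalates | 1 of 6 stops |
|---|---|---|---|
| 10% | 0.91 | 0.906 | 0.729 |
| 20% | 0.71 | 0.709 | 0.512 |
| 30% | 0.49 | 0.494 | 0.343 |
| 40% | 0.31 | 0.309 | 0.216 |
| 50% | 0.17 | 0.172 | 0.125 |
| 60% | 0.08 | 0.082 | 0.064 |
| 70% | 0.03 | 0.032 | 0.027 |
| 80% | <0.001 | 0.0088 | 0.0080 |
| 90% | <0.001 | 0.00103 | 0.00100 |

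To the two decimals printed, the entries from 10% to 60% fit only the escalation rule, and so do both worked examples. The 70% entry fits both. The gap between the rules is largest at 20%, where b = 0.197.

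**Step 2: a separate misprint.** The row in 10.5 ends "0.17 | 0.08 | 0.03 | <0.001 | <0.001". The 80% value is wrong under either rule: it should be 0.009 (0.008 if 1 of 6 stops). The 90% value differs only by rounding.

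**Step 3: how often the branch is met.** This needs DLT rates by level, which the documents do not give. I assume one flat rate over all seven levels. The first 1-of-6 result occurs after k levels passed with 0 of 3, so

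P(branch met at least once) = Σ aᵏb, k = 0 to 6.

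This is the same under both readings. The limit of 24 does not bind, because the longest path to a first 1-of-6 result uses 6 × 3 + 6 = 24 participants.

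| Flat DLT rate | 1% | 2% | 5% | 10% | 20% | 30% |
|---|---|---|---|---|---|---|
| Branch met | 0.18 | 0.32 | 0.54 | 0.58 | 0.40 | 0.23 |

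**Step 4: what the stop reading would do.** The probability of treating anyone at Level 7 is as follows.

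- *No enrolment limit:* (a + b)⁶ if 1 of 6 escalates, a⁶ if it stops.
- *First three Level 7 participants within 24:* if j lower levels used six, 18 + 3j + 3 ≤ 24, so j ≤ 1. The probability is a⁶ + 6ba⁵ if 1 of 6 escalates, and a⁶ if it stops.
- *Six at Level 7 within 24:* j must be 0, so both readings give a⁶.

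| Flat DLT rate | No limit: escalate / stop | First three within 24: escalate / stop | Six within 24: either |
|---|---|---|---|
| 5% | 0.85 / 0.40 | 0.72 / 0.40 | 0.40 |
| 10% | 0.55 / 0.15 | 0.37 / 0.15 | 0.15 |
| 20% | 0.13 / 0.02 | 0.06 / 0.02 | 0.02 |

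I also enumerated every path, opening a cohort of three only if it fits within 24 and leaving out the expansion to six at the MTD. The mean highest level treated falls from 6.3 to 4.6 at 5%, from 5.1 to 3.3 at 10%, and from 3.0 to 2.0 at 20%.

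**The case against.** The strongest reply is that the documents already point to one answer. The standard 3+3 label appears repeatedly. In 6.1.2 both true stop outcomes end the study and name the prior dose as MTD, while the 1-of-6 sentence does neither and has the dose as its subject. Section 8.5.1 says the stopping rules are in 8.4, and 8.4 does not list 1 of 6. Section 10.4.3 accepts 1 of 6 at the MTD, and 10.5 counts it as escalation. On this view there is one wrong word, and a lasting error is unlikely.

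Most of that stands. It makes *escalated* the probable intent, and it means the contradiction exists only on the stop reading. It does not supply the missing instruction: 8.4, 8.5.1 and the 10.4.3 definition are compatible with opening the next level, but none directs it, and 10.5 implies it only through arithmetic.

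The second reply is that the Level 7 figures are illustrative. That is right. They rest on a flat rate over freeze times of 1 to 30 seconds and apply only to the less likely reading. They show no difference if a full six at Level 7 must fit within 24. The comparison in Step 1 needs none of these assumptions.

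The 80% and 90% entries and the cross-reference are clerical and add nothing to the seriousness of the point.

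**Conclusion.** The point holds. The 1-of-6 branch of 6.1.2 is wrong as written: its verb does not fit a standard 3+3, and it leaves escalation, MTD and study status unstated. The rule behind 10.5 is clear from the exact calculation. If 1 of 6 stopped escalation, the printed probabilities would be too high by 18 points at a 10% DLT rate, 20 at 20% and 15 at 30%.

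The harm is conditional. If staff read the sentence as move on, the trial runs as 10.5 describes. If they read it as stop, they reach lower freeze times, by the amounts in Step 4 under the flat-rate assumption. I would still require the correction before use, because this is an operative dosing rule in a first-in-human study and the branch is likely to be met at DLT rates of 5% to 10%. The misprinted 80% entry has no effect on the design.

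**What to change.** In 6.1.2, state that after 1 DLT in 6 the dose is escalated to the next level or, at Level 7, that level is deemed the MTD. The Level 7 clause is an addition, since 6.1.2 has no rule for the top level, but it agrees with the MTD definition in 10.4.3. The outcome of no DLT in three at Level 7 is also unaddressed and could be settled in the same edit.

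In 10.4.3, change the cross-reference from 6.1.1 to 6.1.2. In 10.5, print 0.009 for 80% and 0.001 for 90%.

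If stopping at 1 of 6 is really intended, the changes are larger:

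- name the MTD for that branch in 6.1.2;
- replace the row in 10.5 with (1 − p)³, that is 0.73, 0.51, 0.34, 0.22, 0.13, 0.06, 0.03, 0.008, 0.001;
- change the worked examples to 0.06 at 60% and 0.73 at 10%;
- drop the standard 3+3 label.

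The first option costs one sentence, one cross-reference and two table entries. It adds no patients or procedures to the design that 10.5 describes.

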8.4 Study Halting Rules

If 2 or more participants experience DLT at any dose level, then the prior dose will be determined to be the MTD and the study will be terminated. Participants already enrolled in the study will be followed post procedure as per protocol. The study will be terminated in the event of death, massive hemoptysis, or acute respiratory distress syndrome (ARDS).

Additionally, the study will be suspended when three grade 3 AEs determined to be "probably related.". The medical monitor will notify the investigators immediately when the third grade 3 event is reported and enrollment screens will stop accepting new study participants. The investigators will inform the DSMB members within 24 hours of this occurrence and will provide the DSMB with AE listing reports. The DSMB will convene an ad hoc meeting by teleconference or in writing as soon as possible. The DSMB will provide recommendations for proceeding or halting the study.

8.5 Safety Oversight:

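### Section 6.1.2 terminates a dose after 1 of 6 DLTs with no next step, against 10.4.3 and the 10.5 table; and 10.4.3 lets a cleared Level 7 be called the MTD on three participants

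*Combined protocol and SAP*

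**What the plan says.** Section 6.1.2 describes the design as a standard 3+3 over seven freeze times, from 1 to 30 seconds. Its branches are:

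- 0 of 3: "If none of the first three participants at a given dose experiences dose-limiting toxicity (DLT), the dose will be escalated".
- 1 of 3: three more are enrolled at the same dose.
- 1 of 6: "If among these six, only one experiences DLT, the dose will be terminated".
- Two or more of 3, or two or more of 6: the prior dose is the MTD and the study ends. Section 8.4 repeats this: "the prior dose will be determined to be the MTD and the study will be terminated".
- If the MTD has been reached with only three treated there, "an additional three will be treated to ensure six subjects are treated at the MTD".

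Section 10.4.3 says the MTD "will be determined based on the dose escalation rules described below and in Section 6.1.1", and then gives a criterion: "The MTD is the dose at which fewer than 1 of 3 or at most 1 of 6 participants" on that dose have a DLT. Section 10.5 tabulates the probability of escalation by true DLT rate, for example: "If the true DLT rate is 10%, the probability of escalation is 0.91". On sample size, the Protocol Summary says "Up to 24 participants", while 10.5 says approximately 24, with the exact number set by the escalation.

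**The concern.** Determining the MTD is a primary objective (section 3.1), and 10.4.1 says the study is designed for it. Two parts of the rule do not fit together.

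1. After 1 of 6, the operative section tells the team to terminate the dose and does not say whether the next level opens. The rest of the plan implies that it does. In a first-in-human trial this sentence decides whether the next cohort is exposed, and no other section corrects it.

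2. The 10.4.3 criterion is really a rule for passing a level, and several levels can meet it at once. After a failed level, the prior-dose rule settles which one is meant. If Level 7 clears, nothing does: 6.1.2 and 8.4 name an MTD only as the dose below a failing one, yet Level 7 meets the 10.4.3 criterion, possibly on 0 of 3. Whether the expansion to six would then apply is also unclear, because it is triggered by reaching an MTD that 6.1.2 has not named. Section 3.1 hypothesises that every planned level will be safe, so this is the outcome the protocol expects.

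**Working it through.** **Which rule produces the 10.5 table?** Let p be the true DLT rate at a level.

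- P(0 of 3) = (1−p)³
- P(1 of 3, then 0 of the next 3) = 3p(1−p)² × (1−p)³ = 3p(1−p)⁵

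If 1 of 6 escalates, P(escalation) is the sum. If 1 of 6 ends escalation, it is the first term alone. At p = 10%: 0.729 + 0.177 = 0.906, against 0.729.

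| True DLT rate | 10.5 table | 1 of 6 escalates | 1 of 6 ends escalation |
|---|---|---|---|
| 10% | 0.91 | 0.906 | 0.729 |
| 20% | 0.71 | 0.709 | 0.512 |
| 30% | 0.49 | 0.494 | 0.343 |
| 40% | 0.31 | 0.309 | 0.216 |
| 50% | 0.17 | 0.172 | 0.125 |
| 60% | 0.08 | 0.082 | 0.064 |
| 70% | 0.03 | 0.032 | 0.027 |

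The entries at 10% to 60% match only the escalating rule; 70% rounds to 0.03 under both. As a side note, the table's <0.001 at 80% fits neither rule (0.009 or 0.008), and at 90% both give about 0.001. That does not affect this point.

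**How often does the 1-of-6 branch arise?** The first such cohort appears at a level when all lower levels cleared on 0 of 3. So P(at least one) is the sum over levels of [product of (1−p)³ over lower levels] × 3p(1−p)⁵. For a flat rate, with q = (1−p)³ and m = 3p(1−p)⁵, this is m(1−q⁷)/(1−q). At 10%: 0.17715 × (1 − 0.1094)/0.271 = 0.582.

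The documents give no DLT rates for BCI, so these profiles are assumptions:

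| Assumed profile | P(a 1-of-6 cohort occurs) |
|---|---|
| Flat 1% | 18% |
| Flat 2% | 32% |
| Flat 3% | 42% |
| Flat 5% | 54% |
| Flat 10% | 58% |
| Flat 20% | 40% |
| Flat 30% | 23% |
| Rising 2, 3, 5, 10, 20, 30, 40% | 51% |
| Rising 5, 5, 10, 15, 25, 35, 50% | 53% |
| Rising 10, 20, 30, 40, 50, 60, 70% | 39% |

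A limit of 24 does not change these figures, because the first 1-of-6 cohort needs at most 6 × 3 + 6 = 24 participants.

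**How often does Level 7 clear, and on how many?** With 1 of 6 escalating, P(all seven clear) is the product of the per-level escalation probabilities. At a flat 10% it is 0.90615⁷ = 0.50. The share with 0 of 3 at Level 7 is (1−p)³ divided by the escalation probability there: 0.729/0.906 = 0.80. Under a hard limit of 24, seven levels of three use 21, so only one expansion fits.

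| Assumed profile | All clear, no limit | All clear, hard limit of 24 | Level 7 on 0 of 3 (share of all-clear, no limit) |
|---|---|---|---|
| Flat 5% | 83% | 66% | 88% |
| Flat 10% | 50% | 30% | 80% |
| Rising from 2% to 40% | 9% | 5.7% | 70% |
| Rising from 5% to 50% | 3% | 1.5% | 73% |

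The exact two-sided 95% upper limit for the DLT rate is 1 − 0.025^(1/3) = 0.71 after 0 of 3 and 1 − 0.025^(1/6) = 0.46 after 0 of 6.

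**The case against.** The strongest reply is that the 1-of-6 sentence is a one-word slip that nobody would follow: the standard 3+3 label, 10.4.3 and 10.5 all point to escalation. That is probably right about intent. It still leaves the operative section wrong and uncorrected, since 8.4 covers only two or more DLTs.

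A reader might go further and infer that 6.1.2, read literally, stops the trial after 1 of 6. The text does not support that. Its failure branches terminate the study and name an MTD; the 1-of-6 branch terminates only the dose and names none. Closing enrolment at that dose and ending escalation are both possible readings, so the right-hand column of the first table shows one reading, not the rule itself.

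A reader might also infer that the branch arises in most trials. That holds for some assumed profiles, but not at flat rates of 1% to 3% or of 20% to 30%.

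On 10.4.3, one might infer that it overrides the six-participant requirement, or that the plan has no step-down rule. Neither stands in general. Section 10.4.3 defers to the escalation rules; 6.1.2 requires six at the MTD and moves to the prior dose at two or more of six; 8.4 applies that at any level; and 10.4.6.1 mentions de-escalation. The citation of 6.1.1 is clerical, because 6.1.2 follows directly. If Level 1 fails, the study ends with no prior dose, and saying so changes no conduct. DLTs are already to be tabulated by level (10.1, 10.4.3). What remains of the second part is the cleared Level 7.

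**Conclusion.** The point holds in two parts and should be fixed.

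First, the 1-of-6 instruction in 6.1.2 contradicts 10.4.3 and the 10.5 table and leaves the next step unstated. The contradiction with the table needs no assumption about DLT rates. If the sentence were applied as ending escalation, the per-level probability of escalation would fall from 0.91 to 0.73 at a 10% DLT rate, from 0.71 to 0.51 at 20%, and from 0.49 to 0.34 at 30%. How often the branch is met, roughly 18% to 58% of trials, depends wholly on the assumed profiles.

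Second, 10.4.3 permits a cleared Level 7 to be declared the MTD on three participants when 6.1.2 and 8.4 declare none. This affects what is reported and how much data it rests on; it does not show that a wrong dose would be selected. Its frequency is also assumption-dependent: large if DLT rates stay near 5% to 10%, small if they rise steeply. The hard-limit figures treat 24 as strict, which 10.5 does not clearly do.

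**What to change.** - In 6.1.2, in the 1-of-6 branch, replace terminated with escalated.
- In 10.4.3, define the MTD as the highest dose with six treated and at most 1 of 6 with a DLT, lying below a level with two or more DLTs.
- State that if Level 7 clears, the MTD was not reached, and that 30 seconds is reported as the highest level studied, with its DLT count and exact confidence interval.

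Optional clarifications: cite 6.1.2 instead of 6.1.1 in 10.4.3; say explicitly that the MTD steps down if expansion to six brings two or more DLTs; and say that if Level 1 fails, no tolerated dose was identified.

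The cost is a wording amendment to two sections. No procedures are added, since six at the MTD and the two-of-six rule are already in 6.1.2, and the main 10.5 entries already assume escalation after 1 of 6.
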